Prior to initiating this study, all participating investigators and support staff will conduct a protocol initiation meeting to ensure adequate knowledge of the study objectives, procedures, populations, and human subject protections. A log of meeting attendees will be maintained. The team of investigators includes anesthesiologists with expertise in anesthesia for ambulatory procedures, surgeons, and a biostatistician. A study physician will be available at all times for subjects to call regarding potential adverse effects related to the study drug.

The surgical co-investigators perform approximately 12 ambulatory surgical procedures requiring general anesthesia a week, and slightly less than half of those patients are less than 50 years old. By this estimation, there should be approximately 6 eligible patient per week, or 312 eligible patients in a year.

The Investigational Drug Service within the Mount Sinai Hospital Department of Pharmacy will be utilized to randomize consented patients to receive olanzapine versus placebo, and to supply the appropriate medication on the day of surgery.

5) Study Design

a) Recruitment Methods

Patients who consent to and are scheduled to undergo ambulatory surgery at Mount Sinai will be invited by their physician to participate in the study prior to the scheduled date of surgery at their routine preoperative visit at their physician's office. Office locations where recruitment will occur include: the Mount Sinai OB/GYN Ambulatory Department at 1 [REDACTED], the OB/Gyn Mount Sinai Faculty Practice Associates (FPA) at [REDACTED] Upper East Side Gynecology at [REDACTED], Gramercy Gynecology at [REDACTED], New York Physicians at [REDACTED], and the Plastic and Reconstructive Surgery Office at [REDACTED]. A flyer describing the study will be displayed at the first two clinic locations to advertise the study to potential participants. The flyer will instruct interested patients to discuss the study with their gynecologist, or to contact the principal investigator directly. If a patient tells their physician that they are willing to participate, a study investigator will describe the study in detail, answer questions, confirm participant understanding, and provide the written informed consent form for review. If the patient agrees, written informed consent will be obtained at this visit, with opportunity for the subject to withdraw at any time prior to the surgical procedure.

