The majority of PONV interventions in use in current clinical practice reduce the risk by approximately 20%. This reduction is additive when multiple interventions are used. Assuming a 37% incidence of PDNV based on previous literature, to be powered to find a 20% reduction in risk from baseline the study must include 140 patients.

d) Study Timelines

Patients who consent to and are scheduled to undergo ambulatory surgery at Mount Sinai will be invited by their physician to participate in the study prior to the scheduled date of surgery at their routine preoperative visit. If a patient expresses interest in the study after viewing the recruitment flyer, arrangement will be made for an investigator to meet with the patient in clinic prior to the scheduled surgery to explain the study, screen the patient for eligibility, and obtain consent if appropriate. Patients who are consented will be randomized prior to their planned surgery. They will be followed for postoperative nausea and vomiting for 24 hours after discharge by telephone call on post-operative day one.

	Protocol Title:	Olanzapine for the treatment of Post-Discharge Nausea and Vomiting after Ambulatory Surgery
	Principal Investigator Name/Contact Info:	[name] [contact]
	Primary Contact Name/Contact Info:	[name] [contact] [name] [contact]
	Date Revised:	1/31/2018
	Study Number:	GCO#15-1297; HSM# 15-00501

Based on the enrollment within the first year of the study, we expect to have 20-30 patients complete the study per year. Assuming that enrollment continues at the current pace, it will take approximately five years to enroll the necessary 140 patients. As patients only need to be followed for 24 hours after discharge to be assessed for all primary and secondary endpoints, we estimate the study will be complete within 2 weeks of final patient enrollment.

e) Study Endpoints

Primary Objective: Compare the rate of post-discharge retching/vomiting or nausea in patients who receive olanzapine versus placebo.

Secondary Objectives:

- i) Measure the rate of post-discharge retching/vomiting in patients who receive olanzapine versus placebo.
- ii) Measure the rate of post-discharge nausea in patients who receive olanzapine versus placebo.
- iii) Measure the severity of post-discharge nausea in patients who receive olanzapine versus placebo using an 11-point Likert scale.

f) Procedures Involved in the Human Research

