Upon entering the operating room, after application of standard monitors, midazolam 2 mg will be administered for anxiolysis. If endotracheal intubation is indicated, general anesthesia will be induced using fentanyl 3-5 mcg/kg and propofol 1.5-2.5 mg/kg and muscle relaxation achieved with succinylcholine 1-2 mg/kg or rocuronium 0.6 mg/kg, at the discretion of the attending anesthesiologist. Rocuronium will be administered as needed to maintain muscle relaxation during the case. If a laryngeal mask airway is to be used rather than an endotracheal tube, anesthesia will be induced with propofol 1.5-2.5 mg/kg. Regardless of method of airway management, anesthesia will be maintained with sevoflurane at concentrations deemed appropriate by the anesthesia provider based on intraoperative hemodynamic and respiratory monitoring. Additional doses fentanyl will be administered also as deemed appropriate by the anesthesia provider based on intraoperative hemodynamic and respiratory monitoring. All patients will receive dexamethasone 8 mg immediately following induction, and ondansetron 4 mg and ketorolac 30mg approximately 30 minutes prior to emergence from anesthesia unless there is a specific contraindication. Intubated patients will receive neuromuscular blockade reversal with neostigmine 0.4-0.7 mg/kg prior to tracheal extubation.

	Protocol Title:	Olanzapine for the treatment of Post-Discharge Nausea and Vomiting after Ambulatory Surgery
	Principal Investigator Name/Contact Info:	[name] [contact]
	Primary Contact Name/Contact Info:	[name] [contact] [name] [contact]
	Date Revised:	1/31/2018
	Study Number:	GCO#15-1297; HSM# 15-00501

In the PACU, as needed ondansetron will be ordered as per the department standard orderset, (ondansetron 4 mg intravenous every 4 hours). However, the standard prochlorperazine 10 mg intravenous once will be removed from the orderset to reduce the risk of neuroleptic malignant syndrome or extrapyramidal symptoms when administered in combination with olanzapine. The patients' experience of nausea and/or vomiting will be assessed at 30, 60, and 120 minutes after surgery by trained study personnel. PACU EPIC records will also be audited to record the need for rescue antiemetic medications.

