Prior to discharge from the PACU, subjects will be assessed for signs of orthostatic hypotension (a decrease of 20 mmHg in systolic blood pressure or 10 mmHg in diastolic blood pressure upon standing). Patients who meet the criteria for orthostatic hypotension will be evaluated and treated with intravenous fluid administration. Upon discharge, patients who had symptoms of orthostatic hypotension will be instructed to ambulate with assistance for the first 24 hours after discharge.

Information entered into the subjects' diary will be obtained during a telephone interview on the afternoon or evening of the first day following surgery. At this time investigators will also screen for adverse events.

Relevant preoperative, intraoperative, and postoperative data will be obtained from the anesthesia record, the EPIC electronic medical record, and the telephone interviews and collected on standardized forms by trained study personnel.

Data to be collected:

Age
BMI
ASA status
Smoking status
History of PONV
History of motion sickness
Total intraoperative fentanyl (mcg)
Total intraoperative propofol (mg)
Total intraoperative rocuronium (mg)
Total intraoperative neostigmine (mg)
Total intraoperative Sevoflurane
Duration of surgery
Total fentanyl dose in PACU (mcg)

	Protocol Title:	Olanzapine for the treatment of Post-Discharge Nausea and Vomiting after Ambulatory Surgery
	Principal Investigator Name/Contact Info:	[name] [contact]
	Primary Contact Name/Contact Info:	[name] [contact] [name] [contact]
	Date Revised:	1/31/2018
	Study Number:	GCO#15-1297; HSM# 15-00501

Total oxycodone dose in PACU (mg)
Rescue antiemetics in PACU (yes/no)
Ondansetron total dose (mg)
Length of PACU stay (minutes)
Vomiting in PACU (#episodes at least 1 min apart)
Nausea in PACU (highest number reported on 11 point Likert scale)
Post-discharge vomiting (#episodes at least 1 minute apart)
Post-discharge nausea (highest number reported on 11 point Likert scale)

g) Specimen Banking

N/A

h) Data Management and Confidentiality

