[name] and [name] are board certified anesthesiologists with expertise in the perioperative management of patients. All subjects will be called on post-operative day one by a study investigator. In addition to the routine post-operative day one phone call to the patient, all participants will receive instructions and a business card in order to have a point of contact to report a potential adverse event at any time during or after the study period. They will also be specifically informed that they should receive emergency department care for any signs and symptoms of hypotension. Patients who will not have anyone present at home after discharge will receive a same-day follow-up phone call from the study team to screen for adverse events.

The study remains blinded during the second year of enrollment and no interim analysis of efficacy has been performed. No adverse events have been reported by any study participants.

All adverse events will be recorded by the research team in a non-anonymized fashion and reported directly to the Mount Sinai Institutional Review Board.

The study team will report the following to the Institutional Review Board and FDA within 5 business days of when they became aware of the event:

Any event that, in the principal investigator's opinion, is unexpected and at least probably related to the study.

Any event that is expected but occurring with greater frequency/intensity will be reported to the Institutional Review Board and FDA within 5 business days.

	Protocol Title:	Olanzapine for the treatment of Post-Discharge Nausea and Vomiting after Ambulatory Surgery
	Principal Investigator Name/Contact Info:	[name] [contact]
	Primary Contact Name/Contact Info:	[name] [contact] [name] [contact]
	Date Revised:	1/31/2018
	Study Number:	GCO#15-1297; HSM# 15-00501

The study team will report the following to the IRB and FDA on an annual basis:

All expected adverse events

The principal investigator will not enroll any new patients until the IRB has reviewed and responded to the report. The study team will continue to follow patients who are already enrolled.

Enrollment will continue once the IRB approves.

j) Withdrawal of Subjects

Patients may be withdrawn from the study without their consent if their eligibility changes from the time of initial consent to the start of surgery or, if in the opinion of the investigator, they are not appropriate for olanzapine administration.

6) Risks to Subjects

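### The neostigmine reversal dose (0.4-0.7 mg/kg) is probably ten times too high as written and should be verified and corrected before further enrolment

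*Combined protocol and SAP*

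**What the plan says.** The anesthetic procedure is set out in section 5 f) of the combined protocol and SAP. For reversal of the muscle relaxant it states: "Intubated patients will receive neuromuscular blockade reversal with neostigmine 0.4-0.7 mg/kg prior to tracheal extubation". This is the only neostigmine dose in the available text. The list of data to be collected, later in the same section, includes the total intraoperative neostigmine in mg, which neither confirms nor corrects the per-kilogram figure.

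The neostigmine sentence leaves no room for judgement, while its neighbours do. The choice of relaxant, for example, is left open: "muscle relaxation achieved with succinylcholine 1-2 mg/kg or rocuronium 0.6 mg/kg, at the discretion of the attending anesthesiologist". Sevoflurane and additional fentanyl are left to the anesthesia provider, and the antiemetics and ketorolac may be withheld when contraindicated.

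Three other statements bear on the point:
- Section 4 (Resources): "The team of investigators includes anesthesiologists with expertise in anesthesia for ambulatory procedures".
- Section 5 d) (Study Timelines): "we expect to have 20-30 patients complete the study per year", towards a target of 140.
- The safety monitoring text shortly before section 5 j): "The study remains blinded during the second year of enrollment", and "No adverse events have been reported by any study participants".

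**The concern.** The written range looks about ten times too high for this drug. Both ends have the digits expected of a usual reversal range, but with the decimal point one place to the right. That pattern suggests a typing slip.

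If so, the text is wrong whether or not staff follow it. Followed literally, it would give intubated patients in both arms a several-fold overdose. If staff ignore it and give a usual dose, every reversed patient departs from the protocol. The issue is patient safety and the correctness of an operative instruction. It does not touch the inference, because the same sentence governs both arms.

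**Working it through.** **Inputs from the document.** Neostigmine 0.4-0.7 mg/kg (section 5 f); target 140 patients (section 5 c); 20-30 completers a year (section 5 d); second year of enrolment (safety monitoring text).

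**Inputs assumed.** Body weights of 50, 70 and 100 kg, since the document gives none. A usual reversal dose of about 0.03-0.07 mg/kg, with the upper end widened to 0.10 mg/kg as a sensitivity check. Neither dose figure is in the document.

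**Step 1: total dose = mg/kg × weight.**

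| Weight (assumed) | As written, 0.4-0.7 mg/kg | Assumed usual, 0.03-0.07 mg/kg | Decimal moved, 0.04-0.07 mg/kg |
|---|---|---|---|
| 50 kg | 20-35 mg | 1.5-3.5 mg | 2.0-3.5 mg |
| 70 kg | 28-49 mg | 2.1-4.9 mg | 2.8-4.9 mg |
| 100 kg | 40-70 mg | 3.0-7.0 mg | 4.0-7.0 mg |

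**Step 2: written minimum against usual maximum, per kg.** This comparison does not depend on weight.
- 0.4 / 0.07 = 5.7.
- With the maximum widened: 0.4 / 0.10 = 4.0.
- For the written range merely to touch the usual range, the usual maximum would have to be 0.4 mg/kg.

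**Step 3: does a one-place shift explain it?** 0.4 becomes 0.04 and 0.7 becomes 0.07. Both ends then lie inside 0.03-0.07 mg/kg.

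**Step 4: patients still to come (projection at the stated pace).**
- Start of year 2: 140 − 30 = 110 to 140 − 20 = 120.
- End of year 2: 140 − 2 × 30 = 80 to 140 − 2 × 20 = 100.

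These are upper bounds on those exposed to the instruction, because it covers intubated patients only and the share intubated is not given.

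**Step 5: a cut for an optional look-back at recorded totals.** The assumed usual maximum at 100 kg is 0.07 × 100 = 7 mg. The written minimum exceeds 7 mg at any weight above 7 / 0.4 = 17.5 kg, so literal use would be flagged in any adult (at 45 kg, 0.4 × 45 = 18 mg). The cut is imperfect in both directions. At 120 kg a usual dose can reach 0.07 × 120 = 8.4 mg and be flagged. At 50 kg the usual maximum is 0.07 × 50 = 3.5 mg, so a total between 3.5 and 7 mg would exceed it without being flagged.

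**The case against.** The strongest objection is that the document does not contradict itself. It holds no reference dose, so the sentence becomes an error only through an assumption brought from outside, and both multiples (5.7 and 4) rest on it. This stands, and it is why the error is called probable and the first action is verification. The conclusion is not sensitive to the exact figure, however: the assumed maximum would have to be wrong by a factor of nearly six before the ranges met.

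Second, the text was read from a PDF by a program, and a reading error cannot be fully excluded. It is unlikely, since a zero would have to be lost from both ends of the range while other decimals in the same paragraph read normally. Looking at the source is still the cheapest check and should come first.

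Third, urgency. Neostigmine is a background drug, the team includes anesthesiologists, and no adverse events had been reported, so literal use may be unlikely. This lowers the expected harm, though the absence of reports is weak evidence when the number intubated is unknown. It does not make the instruction right.

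Fourth, the enrolment projection counts patients remaining rather than patients at risk, and recruitment status is known only as of the version revised 1/31/2018. The look-back rests on the same dose assumption, and the data list has BMI but not weight, so a per-kilogram judgement needs a chart look-up. These limits are accepted. Neither item is needed to justify correcting the sentence.

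**Conclusion.** The concern holds, with medium confidence, and the sentence must be fixed. As written, intubated patients are to receive 28-49 mg of neostigmine at an assumed 70 kg. If usual doses are 0.03-0.07 mg/kg, the lowest written dose is 5.7 times the highest usual one, and 4 times if the usual maximum is taken as 0.10 mg/kg. A one-place decimal error is the likely cause but is not proven. No exposure to the written dose and no resulting harm has been shown. The rating rests on the instruction itself: a mandatory dose, without qualification, in a protocol under which patients were still being enrolled. Sample size, analysis and the between-arm comparison are unaffected.

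**What to change.** Before further enrolment:
1. Confirm the figure in the source document.
2. Have the anesthesiologist investigators check the range against the approved labelling.
3. Amend the sentence in section 5 f) to the verified mg/kg range, expected to be 0.04-0.07 mg/kg.

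Optionally, review the neostigmine totals already collected and look up in the anesthesia record any total above about 7 mg. A flagged total prompts a look-up and is not in itself evidence of an overdose. A total at or below the cut does not rule out an excess in a lighter patient.

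The cost is a labelling check and a one-line amendment. The optional review uses one variable already on the data list. No extra patients, visits or procedures are needed.

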In the case of PDNV, the use of postoperative opioids is likely a significant contributory factor, as it occurs hours after the anesthetic agents have been metabolized. This is likely why the use of TIVA, which helps prevent PONV, has no effect on the incidence of PDNV. One mechanism of opioid-induced nausea and vomiting is mediated through D₂ receptors in the chemoreceptor trigger zone in the medulla oblongata.¹² This makes anti-dopaminergic agents, such as olanzapine, ideal to target opioid induced nausea and vomiting. The half-life elimination of orally administered olanzapine is 21-54 hours. The time to peak plasma concentration is approximately 6 hours. Therefore orally administered olanzapine, taken with a small sip of water prior to anesthetic induction, demonstrates ideal pharmacokinetics for the prevention of delayed PDNV. Olanzapine's long half-life, low cost, excellent safety profile with short-term use, and targeting of multiple receptors implicated in nausea and vomiting (especially D₂) make it a hopeful prospect for the prevention of PDNV.

3) Setting of the Human Research

This study will be conducted at the Icahn School of Medicine at Mount Sinai. Consent will be obtained at the Mount Sinai OB/GYN Ambulatory Department at [name] Klingenstein Pavilion E level clinic and OB/Gyn Mount Sinai Faculty Practice Associates (FPA) at [name]

Study medications will be administered in the preoperative holding area in the sixth floor of the Annenberg Pavilion at [name]. The intraoperative protocol will take place in the operating room in which the case is scheduled. An investigator will evaluate the patient postoperatively in the Annenberg sixth floor PACU.

4) Resources Available to Conduct the Human Research

	Protocol Title:	Olanzapine for the treatment of Post-Discharge Nausea and Vomiting after Ambulatory Surgery
	Principal Investigator Name/Contact Info:	[name] [contact]
	Primary Contact Name/Contact Info:	[name] [contact] [name] [contact]
	Date Revised:	1/31/2018
	Study Number:	GCO#15-1297; HSM# 15-00501

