Subjects who consent to and are scheduled for ambulatory surgery under general anesthesia will be invited to participate in the study during a routine preoperative visit prior to the day of surgery by a study investigator. The details of the study will be reviewed and written informed consent will be obtained. Additionally, a flyer describing the study will be displayed at the two participating clinic locations to advertise the study to potential participants. The flyer will instruct interested patients to discuss the study with their gynecologist, or to contact the principal investigator directly. If a patient tells their physician that they are willing to participate, a study investigator will describe the study in detail, answer questions, confirm participant understanding, and provide the written informed consent form for review. Patients who have agreed to participate will have a 12-lead electrocardiogram (EKG) obtained in pre-surgical testing. Alternatively, if an EKG is not obtained prior to the day of surgery, it will be performed the same day in the assessment area prior

	Protocol Title:	Olanzapine for the treatment of Post-Discharge Nausea and Vomiting after Ambulatory Surgery
	Principal Investigator Name/Contact Info:	[name] [contact]
	Primary Contact Name/Contact Info:	[name] [contact] [name] [contact]
	Date Revised:	1/31/2018
	Study Number:	GCO#15-1297; HSM# 15-00501

to surgery. Patient's with a QTc > 450 ms using the Fridericia formula will be excluded.

Subjects will be counseled verbally to avoid alcohol, benzodiazepines, and motor vehicle driving for 24 hours following discharge.

The name and date of surgery of the consenting patient will be given to the Investigational Drug Service of the Mount Sinai Pharmacy for randomization and preparation of the medication. On the day of surgery, an investigator will pick up the medication from the pharmacy for the individual subject, and have the subject take the medication with a small sip of water in the preoperative holding area within one hour prior to entering the operating room. In addition, the patient will be provided with a standardized diary to record episodes of vomiting for the first 24 hours after discharge and will be provided with verbal and written instructions for completing the diary (appendix 1). Subjects will be asked for a preferred contact number for the postoperative phone call and permission to leave a voicemail will be requested.

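### Prochlorperazine is withheld in the PACU because of olanzapine, but the visible post-discharge avoid list does not name it (minor safety gap)

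*Combined protocol and SAP*

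**What the plan says.** Section 5) f), Procedures Involved in the Human Research, keeps as-needed ondansetron in the PACU and removes one drug: "However, the standard prochlorperazine 10 mg intravenous once will be removed from the orderset to reduce the risk of neuroleptic malignant syndrome". The sentence goes on to name extrapyramidal symptoms, and ties both risks to use together with olanzapine. Prochlorperazine appears nowhere else in the visible text.

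The visible instructions for the time after discharge are these:

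- Section 5) f): "Subjects will be counseled verbally to avoid alcohol, benzodiazepines, and motor vehicle driving for 24 hours following discharge".
- Section 5) f): patients who had orthostatic symptoms are told to walk with help for 24 hours.
- Section 5), safety follow-up before j) Withdrawal of Subjects: every participant gets instructions and a business card as a contact for adverse events, and is told to seek emergency care for signs of hypotension.

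On pharmacokinetics, section 2) Background states: "The half-life elimination of orally administered olanzapine is 21-54 hours", and: "The time to peak plasma concentration is approximately 6 hours". The dose is swallowed "within one hour prior to entering the operating room". Nausea and vomiting in the PACU "will be assessed at 30, 60, and 120 minutes after surgery by trained study personnel".

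**The concern.** The hazard is the sponsor's own judgement: the plan regards prochlorperazine on top of olanzapine as risky enough to change a standard order set. That reason depends on olanzapine being in the body, not on the patient being in the PACU. Olanzapine was chosen because one preoperative dose should still act at home, so the reason for the precaution goes home with the patient.

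The trial studies nausea at home, where a patient might seek or be given an antiemetic. Followed as written in the visible text, the plan does not prevent a combination that it treats as hazardous. The person most likely to be unaware is a prescriber outside the study team, such as an emergency clinician treating a blinded participant. The visible description of the card gives that person a contact but no drug to avoid.

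**Working it through.** The plan states no figure on this point to reproduce. The check has two parts.

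**1. Scope of the precaution against scope of the post-discharge advice**

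| Place | Setting | Names prochlorperazine? |
|---|---|---|
| 5) f), order set | PACU | Yes, removed |
| 5) f), counselling | 24 h after discharge | No: alcohol, benzodiazepines, driving |
| 5) f), orthostatic advice | 24 h after discharge | No: assisted walking |
| 5), safety follow-up | After discharge | No: contact card, emergency care for hypotension |
| 5) b), exclusion 2 | Entry | No: current antipsychotic use only, so it does not restrict a new prescription after dosing |

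**2. Is olanzapine still present at home?**

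Inputs from section 2): half-life T = 21 to 54 h; peak about 6 h after the dose. Assumption: simple first-order decline from the peak. The fraction of peak left t hours after the peak is 0.5^(t/T).

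- t = 12 h: 0.5^(12/21) = 0.673; 0.5^(12/54) = 0.857.
- t = 24 h: 0.5^(24/21) = 0.453; 0.5^(24/54) = 0.735 (0.7349 before rounding).

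So about 45% to 73% of the peak level remains 24 hours after the peak.

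**Sensitivity to discharge time.** The plan gives no discharge time. Take 0-1 h from dose to operating room (from the plan), an assumed 1-5 h in the room, and 2 h to the last PACU assessment, treated here as discharge. The range is then 0 + 1 + 2 = 3 h to 1 + 5 + 2 = 8 h after the dose. For discharge at d hours, the end of the 24-hour window lies d + 24 - 6 = d + 18 hours after the peak:

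- d = 3 h: 0.5^(21/21) = 0.50; 0.5^(21/54) = 0.76.
- d = 8 h: 0.5^(26/21) = 0.42; 0.5^(26/54) = 0.72.

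Under either assumption a substantial level remains at the end of the existing 24-hour advice. These figures describe the level of drug, not a probability of harm.

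**The case against.** The strongest reply is that the protocol acts where it documents a default exposure. Intravenous prochlorperazine was a standard PACU order, so it was removed. No default order at discharge is documented, and section 2) notes that patients at home have no intravenous antiemetics and mostly do not contact a provider. This stands, and it is why no number of exposed patients can be given.

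Second, part of the text is unseen. The end of the data-management subsection and the start of the safety follow-up, the consent form, appendix 1 and the card's wording are not available. Any of them may already carry the precaution. This also stands, and it limits the point to the visible text.

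Third, there are real safeguards: a protocol initiation meeting and a study physician available at all times (section 4), a day-one call that screens for adverse events, same-day calls to patients who are alone at home, and no adverse events reported by the second year of enrollment. These lower the risk. They mainly inform study staff or respond after an event; in the visible text they do not warn an outside prescriber beforehand.

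Four stronger readings are tempting and not supported:

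- *The plan contradicts itself.* It does not. The counselling list appears aimed at sedation, and leaving a drug off it is an omission.
- *Patients are being given the combination at home.* No document shows this.
- *The level remaining shows that 24 hours is too short.* The documents give no level at which the interaction matters, so they cannot show that 24 hours is too short or too long. An area-under-the-curve argument does no better: it rests on an assumed discharge time and mostly reflects the long half-life.
- *Home antiemetic use goes unasked.* The data list has "Rescue antiemetics in PACU (yes/no" and no matching home item. But it also omits adverse events and the orthostatic result, which the same section requires to be assessed, so it is not exhaustive.

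**Conclusion.** The point holds as a minor safety gap in the visible text. The sponsor's reason for withholding prochlorperazine still applies after discharge, and the existing avoid list does not name the drug. The size is an exposure statement only: about 45% to 73% of the peak olanzapine level remains 24 hours after the peak, given the plan's half-life range and first-order decline. The number of patients affected is unknown and may be zero. Sample size, power and alpha are not involved. The documents do not settle whether home antiemetic use could bear on the primary endpoint, and this point makes no claim either way.

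**What to change.** Apply the following in both arms, so that blinding is kept:

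1. In section 5) f), add prochlorperazine to the existing 24-hour avoid list, and exclude it from discharge prescriptions for at least the same 24 hours.
2. On the contact card described in the safety follow-up, add a line for outside clinicians: *may have received olanzapine 10 mg or placebo; avoid prochlorperazine; call the study physician*. The discharge-order change does not reach an outside prescriber, but this line can.

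Leave to the clinical team whether the window should be longer and whether other dopamine antagonists belong on the list. A question on the day-one call about antiemetics taken at home (name and time) is optional. If the unseen text already gives the instruction, a cross-reference from section 5) f) is enough.

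The cost is one line each in the counselling script, the discharge orders and the card, with no extra visits or staff. The clinical downside is one fewer rescue option at home, for placebo patients too. The plan already accepts that trade in the PACU for the same reason.
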